**Effects on Respiratory mechanics of two different ventilation strategies during roboticgynecological surgery.**

**Introduction:**

For many years, the mechanical ventilation during general anesthesia has been conducted using high tidal volumes ( $V_t$ ) and without applying Positive End Expiratory Pressure (PEEP). This ventilatory strategy was considered to avoid alveolar collapse to improve ventilation-perfusion mismatch and to reduce the oxygen fraction. The potential harmful effects of short term intra-operative ventilation are increasingly recognized [1]. The mechanical ventilation may cause a pulmonary complication defined Ventilator-Induced Lung Injury (VILI). This respiratory condition is characterized by alveoli overdistension or repetitive opening and closing of atelectatic lung area. Alveolar overdistension could be prevented applying lower  $V_t$  [2] and higher levels of PEEP could prevent alveolar derecruitment [3]. Recently, two conventional meta-analyses of observational studies and randomized controlled trials on intra-operative ventilation have supported the use of lung protective ventilation, with lower  $V_t$  and higher levels of PEEP in order to prevent VILI and postoperative pulmonary complications [4,5]. Further studies are necessary to understand if the outcome improvement was related to lower  $V_t$  or high levels of PEEP. Laparoscopy is a well-established procedure for gynecologic surgery, with an induced pneumoperitoneum to facilitate the laparoscopic manipulation and it is often performed in Trendelenburg position (the head down body position). The increase of abdominal pressure related to both pneumoperitoneum and Trendelenburg position has demonstrated to impair the respiratory function, mainly inducing atelectasis area in the dependent lung regions [6-9]. In case of atelectasis, the distribution of  $V_t$  to the limited amount of functional lung parenchyma may induce alveolar stress and strain. These conditions are the main mechanisms underlying VILI [10-11] and the hypothesis that a protective ventilation has some benefits and should be applied during general anesthesia has been widely demonstrated [6,9,12-15]. Recently, the concept of “lung protective ventilation strategy” has been adapted from acute respiratory distress syndrome to the anesthesiologic management. In fact, the application of an “open lung” strategy, consisting in a recruitment maneuvers (RMs) followed by the consequent application of PEEP has been suggested to be able to improve oxygenation through the re-expansion of pneumoperitoneum-induced atelectasis area. The effects of open lung

ventilatory strategy on respiratory mechanics and postoperative pulmonary complications in healthy patients underwent robotic–laparoscopic surgery in deep Trendelenburg position have not been specifically investigated. The aim of this study was to evaluate the effects of two ventilatory strategies (protective mechanical ventilation versus conventional mechanical ventilation), during general anesthesia in robotic laparoscopic gynecological surgery in deep Trendelenburg position, on respiratory mechanics and postoperative pulmonary complications in healthy patients.

### **Methods:**

The ventilation protocol consisted in volume-controlled mechanical ventilation through Servo I Ventilator, inspiratory to expiratory ratio of 1:2, and a respiratory rate adjusted to normocapnia (end-tidal carbon dioxide partial pressure between 30 and 40 mmHg). Patients were randomly assigned to Standard (SV) or Protective (PV) group. Patients in the SV group received a Vt of 10 ml/kg of Ideal Body Weight (IBW) and a PEEP of 5 cmH2O, patients in the PV group a Vt of 6 ml/kg of IBW and a PEEP of 8-10 cmH2O, associated to recruitment maneuvers (RMs). IBW was calculated according to a predefined formula:  $50 + 0,91(\text{height [cm]} - 152,4)$  for men and  $45,5 + 0,91(\text{height [cm]} - 152,4)$  for women [16]. RMs were performed only in hemodynamic stable conditions and at pre-set moments: after the induction of anesthesia, after any disconnection from the mechanical ventilator, each hour during the surgical procedures and immediately before extubation. RMs were performed in Pressure Control mode as follows: the limit of peak inspiratory pressure was set at 45 cmH2O and the pressure control was set at 30 cmH2O, therefore three consecutive thirty seconds lasting inspiratory pauses were performed. At the end of RMs, respiratory rate, inspiratory to expiratory ratio, inspiratory pause, and Vt were set back at values preceding the RMs.

### **Statistical Analysis:**

All data are expressed as mean  $\pm$  standard deviation (DS). We use the 2 –side T tests to compare the respiratory variables and gas exchange between the two groups tested. The analysis of variance for repeated measures in each group was performed by one-way ANOVA. When detected, post hoc

analysis was performed using Bonferroni Test. P values  $\leq 0,05$  were considered statistically significant.

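### Between-arm t tests on several variables are each judged at 0.05 with no key variable, time or summary fixed, and the within-arm ANOVAs cannot fill the gap

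*Combined protocol and SAP*

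**What the plan says.** The last paragraph of the Introduction states a comparative aim: "The aim of this study was to evaluate the effects of two ventilatory strategies (protective mechanical ventilation versus conventional mechanical ventilation"), "on respiratory mechanics and postoperative pulmonary complications in healthy patients". The Methods section says that patients were randomised to two groups.

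The Statistical Analysis section is the whole analysis plan. On this point it contains four things:

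- Between arms: two-sided "T tests to compare the respiratory variables and gas exchange between the two groups tested".
- Over time: "The analysis of variance for repeated measures in each group was performed by one-way ANOVA".
- Post hoc: directly after the ANOVA sentence, and conditional on something being detected, "analysis was performed using Bonferroni Test".
- Threshold: P values at or below 0.05 "were considered statistically significant".

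The section does not list the respiratory variables or say which one carries the conclusion. It does not say whether the t test is run at one time, at every time, or on a per-patient mean, change or last value. The only schedule in the document is in Methods and is for recruitment maneuvers: "at pre-set moments: after the induction of anesthesia, after any disconnection from the mechanical ventilator, each hour during the surgical procedures", and before extubation. It is not a schedule of measurements or tests.

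**The concern.** The question is whether one strategy differs from the other, and the t tests are the only stated analysis that addresses it. Many different t tests fit the text: any respiratory variable or gas-exchange measure, at any time, on any summary, each at 0.05. Two things follow.

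First, the chance that at least one truly null comparison comes out significant exceeds 5%. A reader cannot tell whether a reported significant result was the planned one or was picked from several.

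Second, the only stated analysis that uses the repeated measurements together is the one-way ANOVA inside each arm. It asks whether a variable changed during surgery in that arm. A significant change in one arm and a non-significant change in the other is not evidence of a difference between strategies, but it is easily read as such.

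**Working it through.** The documents state no error rate, sample size, measurement times or correlations, so there is no figure of the plan's own to reproduce.

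**Inputs from the documents.** Two randomised arms; two-sided t tests; threshold 0.05 for each test. The plural for respiratory variables means at least two, and gas exchange adds at least one, so there are at least three between-arm tests at a single time.

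**Inputs assumed.** 15, 25 or 40 patients per arm; 3 to 6 measurement times; equal correlation of 0.4 to 0.8 between the tested measurements (between variables in step 1, between times within a patient in step 2).

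**1. Minimum from the wording: three tests at one time, all null.**
- Independent: 1 − 0.95³ = 0.143, or 14.3%.
- Correlated 0.4 to 0.8 (simulation, 20,000 trials per setting): 13.1% down to 9.8%.
- If one of the three truly differs, only two can give a false positive: 1 − 0.95² = 0.0975, or 9.8% if independent. If two differ, the rate for the third is 5%.

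**2. One null variable tested at each of 3 to 6 times.**
- Any time significant at 0.05: from 9.8% (3 times, correlation 0.8) to 23.0% (6 times, correlation 0.4).
- Bonferroni across the times: 2.6% to 4.9%.
- One t test on each patient's mean over the times: 4.6% to 5.4%, the nominal level apart from simulation error.

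**3. Comparing significance across the within-arm ANOVAs.** Suppose both arms have the same true change and each within-arm test has power p. The chance that exactly one arm is significant is 2p(1 − p):
- p = 0.3: 2 × 0.3 × 0.7 = 42%
- p = 0.5: 2 × 0.5 × 0.5 = 50%
- p = 0.8: 2 × 0.8 × 0.2 = 32%

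The misleading pattern would therefore be common with no difference between strategies.

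**4. Price of adjustment.** For a difference of 0.5 SD with an assumed 25 per arm, the noncentrality is 0.5 × √(25/2) = 1.768 on 48 degrees of freedom.
- At 0.05 (critical t 2.011): power 41.0%.
- At 0.05/4 = 0.0125 (critical t 2.595): power 21.6%.

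**5. Does averaging gain power?** The SD of a mean over k times is √((1 + (k − 1)r)/k). With k = 3 and r = 0.8 it is √(2.6/3) = 0.931. For differences of 0.5, 0.5 and 0.25 SD the average is 0.417, or 0.417/0.931 = 0.448 standardised. Power is 34.1% with 25 per arm, below the 41.0% of one t test at the peak. At r = 0.4 the same average has 46.2%. The power gain is conditional; the error control is not.

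**The case against.** - **A t test between randomised arms is valid.** This stands. At a fixed time, or on a patient average, it uses the randomised comparison properly and needs no joint model. A reader might infer that the plan is defective because no analysis combines arm and time. The documents do not support that: naming one t test in advance would itself cure the error-rate problem.
- **The complete null is implausible.** This stands in part. Methods sets different tidal volumes (10 versus 6 ml/kg) and PEEP levels (5 versus 8–10 cmH₂O), so some respiratory variables should differ by construction, and rejecting there is no false positive. The rates above apply only to the truly null variables. A reader might multiply variables by times and quote much higher rates: simulating three variables over 3 to 6 times with 25 per arm gives 22.7% to 53.9%. That assumes nothing differs anywhere and that every time is tested, neither of which the documents state, so it should not be used as the size of the problem.
- **The plan does contain Bonferroni.** It does, so it is not free of all multiplicity control. The post hoc sentence has no stated subject, and a wider reading is possible. Its place after the ANOVA sentence favours comparisons within an arm. On any reading, no family or number of tests is given for the t tests.
- **The study may be exploratory.** The plan does not say so, and it applies a significance threshold.
- **It may be too late to prespecify.** Methods and most of the Statistical Analysis section are in the past tense. This limits the remedy but does not remove the gap.

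**Conclusion.** The point holds and should be fixed. Followed as written, the plan gives at least three between-arm tests at 0.05 with no clear adjustment and no designated key result. The only count that comes from the wording is three tests, giving about 10% to 14% for at least one false positive if all three variables are null. The range of about 10% to 23% per variable also rests on assumed times, patient numbers and correlations, and on testing at every time. Both are upper bounds where some variables differ by design. The textual gap depends on none of these assumptions.

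The within-arm ANOVAs can describe change over time but cannot support a statement that one strategy differs from the other.

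It would go too far to say that the plan has no valid between-arm test, that a mixed model is required, or that the change would raise power. The sure gain is error control and a result that can be identified as the planned one.

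**What to change.** In the Statistical Analysis section:

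1. Name one respiratory-mechanics variable, and either one time or one patient-level average during pneumoperitoneum in Trendelenburg, as the single key between-arm contrast. Test it at two-sided 0.05 and report the difference with a 95% CI. List the measurement times so that the choice is unambiguous.
2. List the other between-arm tests (other variables and times), and either apply Holm or Bonferroni across them or label them exploratory.
3. State that the existing Bonferroni sentence applies within arms, if that is what is meant. Label the within-arm ANOVAs descriptive and draw no between-strategy conclusion from them.

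A model with arm, time and arm-by-time fitted to both arms is a reasonable way to obtain the contrast but is optional. A t test on the named time or average is enough.

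The cost is wording and a little analysis work, with no extra patients. The measurements must include the chosen time or window, which the documents do not confirm. The downside is lower power for each adjusted secondary test, as in the fall from 41.0% to 21.6% under the assumptions shown. If the data have already been seen, the key contrast can no longer be prespecified, and the choice must be reported as post hoc.

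### Do the unlisted respiratory variables leave the mechanics comparison open to opposite answers, given tidal volumes of 6 and 10 ml/kg?

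*Combined protocol and SAP*

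**What the plan says.** The Introduction sets the aim: "The aim of this study was to evaluate the effects of two ventilatory strategies", judged on respiratory mechanics and on pulmonary complications after surgery. It gives two mechanisms as background. One is that "Alveolar overdistension could be prevented applying lower" tidal volumes; the other is that "higher levels of PEEP could prevent alveolar derecruitment". It adds that "Further studies are necessary to understand if the outcome improvement was related to lower" tidal volume or to higher PEEP, and it expects recruitment followed by PEEP to "improve oxygenation through the re-expansion of pneumoperitoneum-induced atelectasis area".

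On the settings, the Methods section states: "The ventilation protocol consisted in volume-controlled mechanical ventilation". It continues: "Patients in the SV group received a Vt of 10 ml/kg of Ideal Body Weight (IBW) and a PEEP of 5" cmH2O. The protective (PV) group has 6 ml/kg with PEEP of 8 to 10 cmH2O and recruitment manoeuvres.

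The Statistical Analysis section then applies two-sided t tests "to compare the respiratory variables and gas exchange between the two groups tested". Neither document section itemises these variables, ranks them or gives a measurement time. Driving pressure and compliance are not named in the body text.

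**The concern.** Mechanics variables are not interchangeable when tidal volume is fixed by assignment and differs by arm. Driving pressure reflects both the delivered volume and the state of the respiratory system. Compliance is usually read as describing the system itself. With volumes of 6 and 10 ml/kg, the protective arm starts with a built-in advantage on driving pressure. One set of patients could then show a benefit on one variable and harm on another, and the plan does not say which is the answer. At stake is selective emphasis after the data are seen. A pressure difference produced by the assigned volume might also be read as evidence that collapsed lung had been reopened.

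**Working it through.** The plan states no sample size, effect size or standard deviation, so there is no figure of its own to reproduce. The check is whether two plausible variables can point in different directions, and under what conditions.

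**Inputs from Methods.** Tidal volume is 10 (SV) and 6 (PV) ml/kg IBW. PEEP is 5 (SV) and 8–10 (PV) cmH2O. IBW for women is 45.5 + 0.91 × (height − 152.4).

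**Assumptions, not in the documents.** Driving pressure DP = Vt/C, where C is respiratory-system compliance. Mean IBW and the spread of C are similar in the arms. For illustration, height is 162 cm and SV compliance is 30 ml/cmH2O.

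**Ratio.** Let r be PV compliance divided by SV compliance. Then DP(PV)/DP(SV) = (6/10)/r = 0.6/r.

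| r | 0.6/r | DP favours | Compliance favours |
|---|---|---|---|
| 0.50 | 1.20 | SV | SV |
| 0.60 | 1.00 | tie | SV |
| 0.80 | 0.75 | PV | SV |
| 0.90 | 0.67 | PV | SV |
| 1.00 | 0.60 | PV | tie |
| 1.10 | 0.55 | PV | PV |

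The directions oppose each other only for 0.6 < r < 1. Both end points are ties.

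**In pressure units.** IBW = 45.5 + 0.91 × 9.6 = 54.24 kg, so Vt is 542.4 ml (SV) and 325.4 ml (PV).
- At r = 1, DP is 542.4/30 = 18.1 against 325.4/30 = 10.8 cmH2O.
- At r = 0.8, PV compliance is 24 and DP is 325.4/24 = 13.6 against 18.1. Plateau pressure (DP + PEEP) is 21.6–23.6 in PV against 23.1 in SV.

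**Sensitivity to spread.** For lognormal compliance, the mean of 1/C is (1 + CV²)/mean. With CVs of 20% and 30% in the two arms, the DP ratio shifts by 1.09/1.04 = 1.048. The lower limit then lies between 0.6/1.048 = 0.57 and 0.6 × 1.048 = 0.63. So 60% is not fixed by the assigned volumes alone.

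**What r = 1 means.** Equal measured compliance is not the same as identical lungs. Compliance is measured at different tidal volumes and PEEP in the two arms, and the Introduction argues that both settings act on the lung.

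**Where r is expected to lie.** The Introduction's rationale is re-expansion of collapsed lung in the protective arm. That points to r above 1, where driving pressure and compliance agree in direction. The two-sided test allows r below 1, but nothing in the documents makes it likely.

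**The case for a change.** The strongest reply is that no worsening of the lung is needed for a misreading. At r = 1, driving pressure is still 40% lower in the protective arm, so a t test could be significant and be reported as a lung effect. Plateau pressure can also disagree with compliance when compliance is better. At an assumed compliance of 50 and PEEP of 10, SV plateau is 542.4/50 + 5 = 15.85. PV plateau is 6.51/r + 10, and the two tie at r = 6.51/5.85 = 1.11. Listing the variables would cost little.

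Two parts of this stand. The plan does omit the list, a lead variable and a time point, and it has no stated variable or analysis for the complications half of the aim. A driving-pressure difference is also not by itself evidence of a lung change.

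The rest does not carry a change. The aim compares whole strategies, so a lower driving pressure due to a smaller assigned volume is a genuine part of the strategy's effect. Sorting variables into delivered load and lung property is not clean: driving pressure contains compliance, and end-tidal CO2 is the target to which respiratory rate is adjusted. If the sponsor may let both kinds answer the aim, with no lead variable or time, the freedom to choose after seeing the data remains. Methods is written in the past tense, so a list added now might only describe what was already recorded.

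**Conclusion.** The observation is accurate, but no change to the plan follows. It is a gap in detail that an analyst can fill sensibly: report tidal volume, PEEP, pressures, compliance and gas exchange side by side, as far as they were recorded, and read the pressures in light of the assigned volumes. The t tests are not made wrong by the missing list. The section speaks of variables in the plural and does not promise a single verdict on mechanics, so a disagreement between two of them would be a finding to report.

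The size is a 40% lower driving pressure at equal measured compliance, and opposite directions only for r strictly between 0.6 and 1.0 (lower limit about 0.57–0.63 if the spread differs as above). This rests on driving pressure being Vt/C, on similar IBW in the arms, and on both variables being among those analysed, which the documents do not say. The pressures in cmH2O rest on the assumed height and compliance. Opposite here refers to the sign of the mean difference only.

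### Between-arm t tests are valid but leave out height, which every patient must already supply; adjusting would probably sharpen comparisons of mechanics outcomes that scale with body size

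*Combined protocol and SAP*

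**What the plan says.** The Statistical Analysis section provides two-sided t tests "to compare the respiratory variables and gas exchange between the two groups tested", with P ≤ 0.05 as the significance threshold. It mentions no covariate, baseline adjustment or regression model. Change over time is handled separately within each arm: "The analysis of variance for repeated measures in each group was performed by one-way ANOVA".

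The Methods section states that "Patients were randomly assigned to Standard (SV) or Protective (PV) group". Tidal volume is 10 ml/kg of IBW in the standard arm, and "patients in the PV group a Vt of 6 ml/kg of IBW" applies in the protective arm. It adds that "IBW was calculated according to a predefined formula", which for women is 45.5 + 0.91 × (height in cm − 152.4).

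The outcome domain given in the title and Introduction is respiratory mechanics, together with postoperative pulmonary complications. Individual mechanics variables are not listed, and compliance is not mentioned. The documents give no sample size, allocation ratio, effect size or SD.

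**The concern.** Tidal volume cannot be set as the protocol requires unless height is known. In gynaecological surgery sex is in effect constant, so IBW is a function of height alone. The trial therefore holds, for every patient, a measure of body size that the assigned ventilation cannot change.

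Some mechanics outcomes plausibly depend on body size; compliance in ml/cmH2O is the obvious one, since larger lungs accept more volume per unit of pressure. A two-sample t test treats that predictable spread as noise. If such an outcome is analysed, the confidence interval for the difference between arms is wider than it need be. What is at stake is precision and power in a trial whose size is not stated.

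**Working it through.** The plan states no power or precision figure, so there is none to reproduce. The check asks what height adjustment would be worth.

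**From the documents:** the women's IBW formula, two arms, two-sided tests at 0.05.

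**Assumed, not in the documents:** compliance is analysed in ml/cmH2O and is proportional to IBW; mean height 162 cm, SD 6.5 cm; total compliance CV 20%, 25% or 30%; 20 patients per arm (N = 40), 1:1.

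**Step 1, spread in body size.** IBW is 43.3 kg at 150 cm, 54.24 kg at 162 cm and 66.1 kg at 175 cm; 66.1/43.3 = 1.53. The CV of IBW is 0.91 × 6.5 / 54.24 = 0.109.

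**Step 2, variance explained.** Under proportionality R² = (0.109/CV)², which is 0.30, 0.19 and 0.13 for CV 0.20, 0.25 and 0.30. Widening the assumptions to mean height 160–165 cm, SD 5–7 cm and CV 20–35% gives R² from 0.05 to 0.37.

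**Step 3, net gain.** Estimating the height slope has a cost. The variance of the adjusted difference relative to the unadjusted one is (1 − R²) × (1 + 1/(N − 4)). At N = 40 the second factor is 1 + 1/36 = 1.0278. The gain in equivalent sample size is the reciprocal of the product, minus 1:

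- R² = 0.30: 1/(0.70 × 1.0278) − 1 = 39%
- R² = 0.19: 1/(0.81 × 1.0278) − 1 = 20%
- R² = 0.13: 1/(0.87 × 1.0278) − 1 = 12%
- R² = 0.04: 1/(0.96 × 1.0278) − 1 = about 1%
- R² = 0: 1/1.0278 − 1 = a loss of about 3%

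With 20 patients in total the factor is 1 + 1/16 = 1.0625, and the loss at R² = 0 is about 6%. Adjustment breaks even at R² = 1/(N − 3). That is a correlation of about 0.16 at N = 40 and 0.24 at N = 20.

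**Step 4, power by simulation.** The setting is a 20% difference in compliance with 20 per arm, t test versus linear model with height. The answer depends on how the effect acts. A proportional effect also raises the protective arm's SD by 20%; an additive effect leaves a common SD.

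| Compliance CV | Proportional effect: t test → adjusted | Common SD: t test → adjusted |
|---|---|---|
| 0.20 | 80% → 91% | 87% → 95% |
| 0.25 | 61% → 69% | 70% → 77% |
| 0.30 | 47% → 51% | 55% → 59% |

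These figures carry simulation error of about one percentage point. With no true difference, both methods rejected in about 5% of simulated trials.

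**The case against.** The strongest reply is that nothing here is an error. The arms are randomised, so the unadjusted t test is unbiased and holds its type I error. A reader might infer that a chance imbalance in height is a separate defect. With 20 per arm the difference in mean height has SD 6.5 × √(2/20) = 2.06 cm, which under proportionality moves the compliance contrast by 0.91 × 2.06 / 54.24 = 3.4%. The t test's standard error already allows for that, so it is not a further fault. This part of the objection stands in full.

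Second, the plan names neither compliance nor its unit, and does not say whether it would be indexed to body size. That it would be analysed is an inference from the stated interest in respiratory mechanics. Setting tidal volume by IBW is a dosing rule; it does not assert that measured compliance is proportional to IBW, and strict proportionality is a generous assumption. This stands too, and makes the point conditional.

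Third, a reader might infer that every between-arm test should be adjusted. The documents do not support that. Tidal volume is already scaled to IBW, which removes part of the size effect from airway pressures and may leave almost none in driving pressure. Nothing in the documents suggests that gas exchange tracks height.

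Fourth, adjustment is not free when height is unrelated to the outcome. The cost is small, however: at an assumed standardised difference of 0.8 and 25 per arm, simulated power falls from 0.794 to 0.784 at zero correlation, but rises from 0.791 to 0.884 at a correlation of 0.5. This limits the claim without removing the case for adjusting outcomes that do scale with size.

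**Conclusion.** The point holds as a conditional gain in precision. The plan's t tests are valid. For mechanics outcomes that scale with body size, if any are analysed, they leave unused a covariate that the protocol already requires.

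The range of 12–39% depends on proportionality to IBW, the assumed height distribution and CV, and 20 per arm. None of these is in the documents, and a weak correlation would leave the gain near zero or slightly negative. The statement that precision is certainly lost, or lost across all respiratory and gas-exchange variables, goes further than the documents allow. So would any suggestion that the planned comparison is biased. This is a cheap improvement rather than a correction.

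**What to change.** In the Statistical Analysis section, before any data are seen:

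- List the mechanics variables to be compared, and mark those expected to scale with body size (for example compliance in ml/cmH2O, if it is analysed and not indexed to size).
- For those variables, specify the linear model outcome = arm + height as the between-arm analysis. Report the adjusted difference with its confidence interval, and keep the unadjusted t test as a sensitivity check.
- Keep the t test for gas exchange and for airway or driving pressures.

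The cost is a few lines of wording and one degree of freedom, with a small loss of precision if height proves unrelated to the outcome. It needs no new measurements or patients and does not change how patients are ventilated.

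### The per-group one-way ANOVA is a weak choice for repeated readings: with unequal numbers of readings it either drops patients or ignores pairing, and a mixed model on all readings would do better

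*Combined protocol and SAP*

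**What the plan says.** The Statistical Analysis section has two parts that matter here. Within each arm: "The analysis of variance for repeated measures in each group was performed by one-way ANOVA", followed after a significant result by post hoc comparisons ("analysis was performed using Bonferroni Test"). Between arms, two-sided t tests are used "to compare the respiratory variables and gas exchange between the two groups tested", with no time point named.

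The combined protocol and SAP does not say when respiratory mechanics or gas exchange are read, how many readings each patient has, or whether readings are tied to hours elapsed or to surgical stages. It gives no operation lengths and no rule for patients with fewer readings than others.

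The only hourly schedule is in Methods: "each hour during the surgical procedures and immediately before extubation". That sentence sets the times of recruitment maneuvers. Methods assigns these to the protective (PV) group only and makes them conditional: "RMs were performed only in hemodynamic stable conditions and at pre-set moments". It is a treatment schedule for one arm, not a reading schedule.

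**The concern.** The Introduction gives respiratory mechanics as part of the aim, and the Statistical Analysis section is its whole analysis. A repeated-measures analysis called a one-way ANOVA can be run in two ways, and the plan does not choose.

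- **Classical repeated-measures ANOVA.** It needs every reading from every patient. A patient with one missing reading leaves the analysis.
- **Ordinary one-way ANOVA with time as the factor.** It keeps every value but treats readings from one patient as if they came from different patients.

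The choice matters most if readings are clock-timed and operations differ in length, because a short operation then has no late reading. The first route describes change in long operations only, on fewer patients. The second compares an early mean over everyone with a late mean over long operations. If length is related to the outcome, part of the apparent change over surgery is then a change in who is measured.

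**Working it through.** **No figure to reproduce.** The documents give no sample size, SD, operation length or number of readings. Every input below is an assumption, chosen to show the mechanism.

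**1. Who has a late reading, if readings are hourly.** Take log-normal length with mean 3 h and SD 1 h. Then σ² = ln(1 + (1/3)²) = 0.105, so σ = 0.325, and μ = ln 3 − 0.105/2 = 1.046. The share reaching t hours is 1 − Φ(z), with z = (ln t − μ)/σ.

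| t | z | Share reaching t | Expected of 20 |
|---|---|---|---|
| 2 h | −1.09 | 86% | 17.2 |
| 3 h | 0.16 | 44% | 8.7 |
| 4 h | 1.05 | 15% | 2.9 |

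At mean 2.5 h (SD 0.75 h) the share reaching 3 h is 22%; at mean 3.5 h (SD 1 h) it is 66%.

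**2. Classical route: complete patients only.** With 20 per arm, about 9 are complete through 3 h (binomial 5th to 95th percentile 5 to 12) and about 3 through 4 h (1 to 6). A separate simulation used 30 patients, readings at 0 to 4 h, median length 3 h, log-SD 0.3, between-patient SD 1, within-patient SD 0.5 and no true change. It kept about 5 of 30. The test rejected in 4.0% to 4.7% of runs at length-outcome correlations of 0, −0.3 and −0.5, so it is valid for those left. The loss is in precision and in whom the result describes.

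**3. Ordinary route: all available values.** If log length has correlation ρ with the patient's level (between-patient SD s), the expected late-minus-first difference under no true change is ρ × s × φ(z)/(1 − Φ(z)). With s = 8 ml/cmH2O the last factor is 0.904 at 3 h and 1.564 at 4 h.

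| Size of ρ | Shift at 3 h (ml/cmH2O) | Shift at 4 h (ml/cmH2O) |
|---|---|---|
| 0 | 0 | 0 |
| 0.2 | 0.2 × 8 × 0.904 = 1.4 | 0.2 × 8 × 1.564 = 2.5 |
| 0.6 | 0.6 × 8 × 0.904 = 4.3 | 0.6 × 8 × 1.564 = 7.5 |

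The shift is downward if ρ is negative and upward if it is positive. In the 30-patient simulation the apparent 0-to-4 h change was about 0, −0.45 and −0.75 SD at correlations 0, −0.3 and −0.5. The formula agrees: 0.3 × 1.492 = 0.45 and 0.5 × 1.492 = 0.75.

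**4. Lost pairing, even with complete readings.** With between-patient SD 1 and within-patient SD 0.5, the error variance is 0.5² = 0.25 in the repeated-measures test and 1² + 0.5² = 1.25 in the ordinary test. The ordinary F ratio is therefore about five times too small. With complete readings and no true change, the ordinary test rejected in 0% of runs against a nominal 5%, while the repeated-measures test rejected in 4.8% to 5.6%.

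With clock-timed readings, this loss of sensitivity works against the shift in step 3. The ordinary test rejected in 0.2%, 1.6% and 7.4% of runs at correlations 0, −0.3 and −0.5.

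**5. Does a mixed model help?** In one simulated sample of 2,000 patients (step 1 lengths, patient SD 8, within-patient SD 3, correlation −0.4, no true change), the raw 4 h mean was 5.4 ml/cmH2O below the first reading. A random-intercept model on all readings reduced this to 0.3. When every patient has every reading, the apparent change is about zero at each correlation.

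**The case against.** The strongest reply is that no reading schedule is stated. If readings are taken at stages that every operation passes through, operation length removes no one. This stands, and it makes everything about late readings conditional.

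A reader might infer from the hourly wording in Methods that readings were hourly, and so that late readings exist only for long operations. The documents do not support this. The wording governs maneuvers in one arm, and the same list also names stages (after induction, before extubation). Nor do they give any operation length or its spread; that length varies is plausible, but not shown.

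A reader might also infer that late between-arm t tests are unreliable. In the 20-per-arm illustration, a 3 h comparison on about 9 per arm has a standard error √(20/9) = 1.5 times larger, and power for a 0.9 SD difference falls from 79% to 43%. But the plan names no time point for the t tests, so a late test is hypothetical. If the assigned strategy does not affect operation length, such a comparison loses power but is not biased between arms. Nothing in the documents suggests that it does.

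It is also fair that a repeated-measures label makes the unpaired test the less obvious reading, and that the sign and size of any length-outcome correlation are unknown. What the reply leaves standing is that the stated method is the weaker one under either reading once any reading is missing, and the unpaired reading is inefficient even when none is.

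**Conclusion.** The point holds as an analysis choice worth improving, not as a demonstrated bias. Loss of patients under the classical test requires only missing readings. Loss of pairing under the ordinary test requires nothing beyond the usual differences between patients. A case-mix shift in the time course requires three things together: clock-timed readings, an unpaired ANOVA on all available values, and a relation between operation length and outcome. The documents establish none of the three.

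The percentages and shifts above rest wholly on assumed sample size, reading times, lengths, SDs and correlations. They show how large the effect could be, not how large it is here. The change is recommended because it is cheap and better under either reading of the plan.

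**What to change.** In the Statistical Analysis section, replace the per-group one-way ANOVA with one mixed model for each respiratory or gas-exchange variable. Patient is a random effect; group, time and group-by-time are fixed terms; all available readings are used. The group-by-time term also tests directly whether the time course differs between arms, which separate per-group tests cannot do. Report the number of patients behind each mean.

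Where readings were taken at stages common to every operation, base the main time-course and between-arm comparisons on those, and treat later clock-hour readings as descriptive. This uses what was collected and asks for no new measurements.

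The cost is a little more analysis work, with no extra patients or procedures. Two limits should be stated. The model removes the bias only if the observed readings explain the missing ones. Time under the assigned strategy varies between patients at end-of-surgery readings, so operation length should be reported by arm.
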